7.7.2 Physical Examination

Any clinically significant changes from Baseline will be documented as an AE.

7.7.3 Vital Signs

Blood pressure and pulse will be summarized by treatment group from Baseline through Week 12/ET. Additionally, change from Baseline in vital signs will be summarized at Week 2, 4, 8, and 12/ET. Any clinically significant changes from Baseline will be documented as an AE.

7.7.4 Urine Pregnancy Tests

Urine pregnancy tests results for WOCBP will be presented in data listings by subject.

7.8 SAMPLE SIZE AND POWER CONSIDERATIONS

Approximately 1300 subjects will be randomized into the study in a 1:1 ratio (650 in each arm) at approximately 50 sites in North America. In the previous phase 2 study, the pooled vehicle IGA ‘success’ rate was 7.1% and the pooled SB204 IGA success rate was 13.4%. Using NQuery Advisor v7 (Statistical Solutions, Ltd) to estimate sample size and statistical power, based on a vehicle IGA success rate of 7% and a 6% difference for the SB204 arm, a sample size of 1294 was estimated to have at least 95% power for a two-sided test at the alpha=0.05 level using the continuity corrected chi-square test.

The statistical power for detecting treatment differences in inflammatory or non-inflammatory lesions exceeds 99% once at least 256 subjects are treated in each group. This is based on the following assumptions:

- For inflammatory lesions: vehicle mean change = -7.6, SB204 mean change = -14.1, and a common standard deviation = 17.1
- For non-inflammatory lesions: vehicle mean change = -5.8, SB204 mean change = -11.3, and common standard deviation = 11.8

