4.1.6 Discontinuation/Withdrawal Procedures

A subject may voluntarily withdraw from study participation at any time. If the subject withdraws consent and discontinues from the study, the Investigator will attempt to determine the reason for discontinuation and record the reason in the subject's study records and in the study database. If a subject is withdrawn because of an AE, that AE should be indicated as the reason for withdrawal. In the event of early discontinuation, (i.e., prior to Week 12/Day 84 visit) and whenever possible, the subject should be asked to return to the study center to complete the Week 12/ET evaluations. Subjects who withdraw from the study will not be replaced.

If at any time during the study the Investigator determines that it is not in the best interest of the subject to continue, the subject will be discontinued from participation. The Investigator can discontinue a subject at any time if medically necessary. The Investigator may discontinue a subject's participation if the subject has failed to follow study procedures or to keep follow-up appointments. Appropriate documentation in the subject's study record and the study database regarding the reason for discontinuation must be completed.

All subjects who fail to return to the study center for the Week 12/ET visit will be contacted by telephone to determine the reason(s) why the subject failed to return for the necessary visit or elected to discontinue from the study. If a subject is unreachable by telephone after a minimum of two documented attempts (one attempt on two different days), a certified letter will be sent requesting that the subject contact the Investigator.

Reasons for an Investigator's withdrawal of a subject may include, but are not limited to, the following:

- Safety (e.g., severe adverse reactions, pregnancy);
- Lack of efficacy as determined by the Investigator;
- When the requirements of the protocol are not respected (e.g., significant issues with dosing compliance);
- When a concomitant medication or treatment likely to interfere with the results of the study is reported, or required, by the subject (the Investigator will decide, in consultation with Chiltern whether the subject is to be withdrawn);

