7.4.1 Primary Efficacy Analyses

There are three co-primary efficacy outcomes:

- change in inflammatory lesions counts at Week 12/ET
- change in non-inflammatory lesions counts at Week 12/ET and
- IGA success at Week 12/ET which is defined as an IGA score of clear (0) or almost clear (1) and ≥ 2 grades less than Baseline

All three co-primary outcomes must show superiority over vehicle (p -value ≤ 0.05) in order for efficacy to be demonstrated; therefore no multiplicity adjustments will be made to the co-primary outcome analyses..

Prior to analysis of co-primary outcomes, missing post-Baseline lesion counts and IGA scores results at each visit will be imputed using a Markov chain Monte Carlo (MCMC) multiple imputation methodology. Separate multiple imputation (MI) procedures will be used for each outcome, using Statistical Analysis Software (SAS) procedure MI. Details of PROC MI and options used in the imputation procedures will be provided in a statistical analysis plan. ITT

subjects with only Baseline assessments will have the Baseline value carried forward across all visits.

The primary analyses of the co-primary efficacy endpoints will be performed in the ITT population where missing data have been imputed as described above. Additional analyses of the co-primary outcomes will be performed using the PP population. To access the sensitivity of the primary efficacy results to imputation methods, each co-primary outcome will be analyzed as described above, but with missing data imputed by last observation carried forward (LOCF) and Baseline observation carried forward (BOCF) on the ITT population.

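### Section 7.8's 95% power for IGA success assumes complete data: about 1300 randomized leaves a 0.46% reserve, although the protocol foresees missing Week 12/ET scores and does not replace withdrawals

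*Protocol*

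**What the plan says.** Protocol Section 7.8 sets the sample size: "Approximately 1300 subjects will be randomized into the study in a 1:1 ratio (650 in each arm"). The calculation is "based on a vehicle IGA success rate of 7% and a 6% difference for the SB204 arm", and its result is that "a sample size of 1294 was estimated to have at least 95% power". The section then specifies that this power is "for a two-sided test at the alpha=0.05 level using the continuity corrected chi-square test". The planning rates come from phase 2, where "the pooled vehicle IGA ‘success’ rate was 7.1% and the pooled SB204 IGA success rate was 13.4" per cent. The section gives no missing-outcome rate and no inflation for attrition, and does not say that the power figure assumes complete data.

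Other sections foresee missing outcomes. Section 7.4.1 says that "missing post-Baseline lesion counts and IGA scores results at each visit will be imputed using a Markov chain Monte Carlo (MCMC) multiple imputation methodology", and that ITT "subjects with only Baseline assessments will have the Baseline value carried forward across all visits". Section 4.1.6 adds: "Subjects who withdraw from the study will not be replaced".

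The protocol also limits missingness. The endpoint is IGA success at Week 12/ET, and Table 1 and Section 4.1.6 ask for the Week 12/ET evaluations when a subject discontinues early.

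**The concern.** Section 7.8 attaches its power to 1294 subjects and randomizes about 1300. If 1294 is the number that must each contribute full information, the design has almost nothing in hand for IGA scores that are never obtained.

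The two handling rules in Section 7.4.1 keep such subjects in the denominator but do not restore what was lost. Multiple imputation adds between-imputation variance. Carrying Baseline forward makes the subject an IGA failure in either arm, because success needs a fall of at least two grades, so both success rates and their difference shrink.

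All three co-primary outcomes must succeed. On Section 7.8's own assumptions the lesion-count power at 650 per arm exceeds 99.9%, so IGA success is the limiting outcome and its power is in effect the power of the trial.

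**Working it through.** **Inputs from Section 7.8.** Success rates p1 = 0.07 and p2 = 0.13, difference d = 0.06, mean rate 0.10; two-sided alpha 0.05 (z = 1.960); power 95% (z = 1.645); 650 randomized per arm.

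**Input not in the protocol.** The missing rate m. I assume 5 to 20%, equal in both arms.

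**Step 1: reproduce 1294.** Without continuity correction,

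n = [1.960 × √(2 × 0.10 × 0.90) + 1.645 × √(0.07 × 0.93 + 0.13 × 0.87)]² / 0.06²

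= (0.8315 + 0.6944)² / 0.0036 = 646.8, so 647 per arm and 1294 in total.

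This matches exactly. With the continuity correction that Section 7.8 names,

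n_cc = (n/4) × [1 + √(1 + 4/(n × d))]² = 680 per arm, or 1360 in total.

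So 1294 is the uncorrected number. That discrepancy is a separate point, but it affects the figures below, so both versions are shown.

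**Step 2: the reserve.** 1300 − 1294 = 6 subjects, and 6/1300 = 0.46%.

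**Step 3: power at a given information content.** For n informative subjects per arm, uncorrected,

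power = Φ{[0.06 × √n − 1.960 × √0.18] / √0.1782}.

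For the corrected test, replace n by (n − 1/0.06)²/n. With 650 per arm and nothing missing, power is 95.1% uncorrected and 94.1% corrected. About 1 point is therefore due to the formula and not to missing data.

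**Step 4: allow for missing outcomes.** I use two cases:
- missing outcomes carry no information, n = 650 × (1 − m);
- imputation recovers half of the lost information, n = 650 × (1 − m/2).

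Example for m = 10% with no information: n = 585, and (0.06 × √585 − 0.8315)/√0.1782 = 1.468, so power is 92.9%.

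| Assumed missing | No information, uncorrected | No information, corrected | Half recovered, uncorrected | Half recovered, corrected |
|---|---|---|---|---|
| 5% | 94.1% | 92.9% | 94.6% | 93.5% |
| 10% | 92.9% | 91.5% | 94.1% | 92.9% |
| 15% | 91.5% | 89.8% | 93.5% | 92.2% |
| 20% | 89.8% | 87.8% | 92.9% | 91.5% |

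If every missing outcome counts as a failure (both rates multiplied by 1 − m, 650 per arm), power is 92.6% uncorrected and 91.2% corrected at 10%, and 89.1% and 87.1% at 20%. This is close to the no-information case.

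**Step 5: sensitivity to the planning rates.** With the unrounded phase 2 rates (7.1% versus 13.4%) and no information from missing outcomes, power is 95.5% uncorrected and 94.6% corrected at 5% missing, and 94.5% and 93.4% at 10%.

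**The case against.** The strongest reply is that the sentence in Section 7.8 is a conditional statement about 1294 subjects, and that uncorrected it is exactly right. That is true of the arithmetic. But the section offers the figure as the basis for randomizing about 1300, and does not state the condition of complete data.

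Second, discontinuation is not the same as a missing endpoint. A reader might infer that every withdrawal costs an outcome. The protocol does not support that: the endpoint is Week 12/ET, discontinuing subjects are asked to complete those evaluations, and the listed discontinuation reasons are disposition codes, not a forecast. This lowers the likely missing rate. It does not bring it to zero, since the return visit is requested where possible and loss to follow-up is foreseen.

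Third, imputation can draw on Weeks 2, 4 and 8, so giving it no credit is too harsh. This stands, and is why the half-recovery columns are shown. How much would really be recovered cannot be worked out from the protocol.

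Fourth, the phase 2 difference was 6.3 points and the plan uses 6, which gives some cushion. At the unrounded rates, uncorrected power holds at 5% missing but not at 10%. The protocol does not present this rounding as an attrition allowance. It also does not say how missing subjects were counted in phase 2. If they were counted as failures, the 7% and 13% already include some attrition, and diluting them again would count it twice.

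Finally, a reader might infer that the trial is underpowered and must be enlarged. The figures do not show that: uncorrected power is still about 90% with 20% missing and no help from imputation.

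**Conclusion.** The point holds as an overstated power figure of modest size. At the planning rates of 7% and 13%, uncorrected power falls below 95% once more than about 0.5% of the information is lost, and it is below 95% at every assumed missing rate from 5 to 20%, even if imputation recovers half. The part attributable to missing data alone (uncorrected, against 95.1% with none missing) is 1.0 point at 5% and 2.2 points at 10% with no recovery, and 0.5 and 1.0 point with half recovery. The further drop in the corrected columns includes the separate formula discrepancy, about 1 point with none missing.

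The sizes rest on a missing rate that the protocol does not give, on equal missingness in the two arms, and on phase 2 rates that do not already absorb attrition. The lesion-count co-primaries are not a practical constraint.

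**What to change.** Keep the sample size. In Section 7.8:

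- say that the 95% figure assumes no missing Week 12/ET IGA;
- name the test actually used to obtain 1294, which is the uncorrected chi-square, or recalculate for the corrected test;
- restate power at 650 randomized per arm net of a missing rate that is marked as an assumption. For example: assuming 10% of Week 12/ET IGA scores are missing, power for 7% versus 13% by the uncorrected test is about 93 to 94%, depending on how much imputation recovers. If the corrected test is kept, the matching range is about 91.5 to 92.9%.

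It would also help to state how missing subjects were counted in the phase 2 success rates.

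The cost is one or two sentences and a slightly less favourable stated power. No endpoint, analysis or enrolment number changes.

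### Protocol Section 7.8: under the continuity-corrected chi-square test it names, 1294 subjects give about 94% power at 7% versus 13%, not at least 95%

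*Protocol*

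**What the plan says.** Section 7.8 of the protocol gives the sample-size calculation for IGA success. It is "based on a vehicle IGA success rate of 7% and a 6% difference for the SB204 arm", which means 7% versus 13%. The result is that "a sample size of 1294 was estimated to have at least 95% power for a two-sided test at the alpha=0.05 level", and the method is given as "using the continuity corrected chi-square test".

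The same section fixes the planned size: "Approximately 1300 subjects will be randomized into the study in a 1:1 ratio (650 in each arm"). It also reports the Phase 2 background, with pooled IGA success rates of 7.1% on vehicle and 13.4% on SB204. No inflation for dropout is stated, and Section 4.1.6 says "Subjects who withdraw from the study will not be replaced".

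**The concern.** One sentence states the two rates, the alpha level, the sidedness, the test, the sample size and the power, so it can be checked without any outside figure. A continuity correction makes the chi-square test more conservative and always raises the sample size needed for a given power. The figure of 1294 looked too small for a corrected test with 95% power at these rates.

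IGA success is the endpoint that sets the sample size. Section 7.8 itself puts the power for both lesion counts above 99% with 256 subjects per group, and Section 7.4.1 requires all three co-primary outcomes to succeed. The calculation for IGA success should therefore be reproducible. A reader who follows the sentence as written gets a different number and cannot tell whether the test, the power or the sample size is wrong.

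**Working it through.** **Inputs, all from Section 7.8:** p1 = 0.07; p2 = 0.07 + 0.06 = 0.13; difference d = 0.06; mean rate 0.10; two-sided alpha 0.05 (z = 1.960); power 0.95 (z = 1.645); 1:1 allocation. The total of 1294 is 647 per arm.

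**1. Reproducing 1294: chi-square test without correction**

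n = [1.960 × √(2 × 0.10 × 0.90) + 1.645 × √(0.07 × 0.93 + 0.13 × 0.87)]² / 0.06²

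- First term: 1.960 × √0.18 = 0.8315
- Second term: 1.645 × √0.1782 = 0.6944
- Sum 1.5259; squared 2.3284; divided by 0.0036 = 646.8

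This rounds up to 647 per arm, or **1294 in total**, an exact match. Power is 95.01% at 647 per arm and 94.98% at 646, so 647 is the smallest size that reaches 95%.

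**2. The test the protocol names: chi-square with continuity correction**

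n′ = (n/4) × [1 + √(1 + 4/(n × d))]²

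- n × d = 646.8 × 0.06 = 38.81
- √(1 + 4/38.81) = 1.0503
- n′ = (646.8/4) × 2.0503² = 679.7

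This rounds up to 680 per arm, or **1360 in total**. That is 66 more than 1294 (66/1294 = 5.1%).

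**3. Power of the named test at the stated and planned sizes**

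Power = Φ[(d − 1/n − 1.960 × se0)/se1], with se0 = √(0.18/n) and se1 = √(0.1782/n).

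At n = 647: (0.06 − 0.00155 − 1.960 × 0.01668)/0.01660 = 1.552, so power is 93.97%.

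| Per arm (total) | Corrected, normal approximation | Corrected, exact enumeration | Uncorrected, normal approximation |
|---|---|---|---|
| 647 (1294) | 93.97% | 94.30% | 95.01% |
| 650 (1300) | 94.07% | 94.40% | 95.09% |
| 680 (1360) | 95.01% | 95.31% | – |

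The exact column sums the binomial probabilities of every pair of counts that the corrected test rejects. It also stays below 95% at 1294 and at 1300, so the shortfall is not a product of the approximation.

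**4. Other ways 1294 might have arisen**

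- Unpooled variance: 644 per arm, or 677 with correction.
- Arcsine method: 636 per arm.
- One-sided corrected test: 572 per arm.
- Phase 2 rates, 7.1% versus 13.4%: 600 per arm (1200) without correction, 631 per arm (1262) with it.

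None of these gives 647. Only the uncorrected calculation in step 1 does.

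**The case against.** The arithmetic is not in dispute; the case on the other side concerns weight.

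- **The gap is small.** It is about 1.0 percentage point by the normal approximation and 0.6 to 0.7 by exact enumeration. No design decision turns on 94% against 95%. This stands.
- **The planning rates are rounded more coarsely than the gap.** At the Phase 2 rates of 7.1% and 13.4%, the corrected test has 95.5% power with 647 per arm, so the claim of at least 95% would be true there. With 7% on vehicle, an SB204 rate of about 13.2% would be enough. This shows how little is at stake, but it does not rescue the sentence, which says that it rests on 7% and a 6-point difference.
- **The origin of 1294 is inferred.** The match with the uncorrected test is exact, but the software output is not shown. This also stands, and it bears on the choice of correction. The inconsistency does not depend on it, because the stated power is not reached under the stated test and rates whatever the source of the number.
- **No effect on the trial is shown.** Section 7.8 names this test for the sample-size estimate. Section 7.4.1 specifies multiple imputation in the ITT population for the co-primary outcomes but names no test for IGA success, and Section 7.1 leaves detailed methods to the SAP. The power of the actual analysis is therefore not shown to be below 95%. This stands and limits the finding to the planning statement.

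**Conclusion.** The concern holds, as a minor error. At 7% versus 13% and two-sided alpha 0.05, the continuity-corrected chi-square test has about 94% power with 1294 or 1300 subjects. The stated lower bound of 95% is not met, and rounding up to 1300 does not close the gap. The named test would need 1360 subjects.

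The conclusion rests only on the inputs printed in Section 7.8, equal arms and no loss of subjects. It does not mean that the trial is underpowered in any practical sense or that it should enrol 1360.

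**What to change.** The sponsor should check in the software output which test was run, then correct the sentence in Section 7.8 in one of two ways:

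- If the calculation was uncorrected, name the chi-square test without continuity correction and keep 1294 subjects and 95% power.
- If the corrected test is meant, keep it and state that 1294 to 1300 subjects give about 94% power.

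The first option should be used only once the output confirms it; otherwise the method would be renamed to fit the number. Either way the cost is one sentence. Enrolment, endpoints, alpha and analysis do not change.

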8. INVESTIGATIONAL PRODUCT MANAGEMENT

8.1 RECEIPT OF INVESTIGATIONAL PRODUCT

Novan, or designee, will provide all investigational products to the study sites.

8.2 STORAGE OF INVESTIGATIONAL PRODUCT

Upon receipt from Novan, or Novan’s designee, a study staff member will place all study supplies in a temperature-controlled area. The pumps should be refrigerated (2-8 °C) until dispensed to a subject. Access to study supplies should be strictly limited to the study staff. Neither the Investigator nor any member of the study staff will distribute any of the study supplies to any person not participating in this study.

If a study staff member becomes aware that the study supplies have not been properly handled (i.e., supply arrives and was not placed in refrigerator upon receipt), the Chiltern CRA must be contacted immediately. In such an event, study supplies should be quarantined and not be administered to any subject until Novan provides further direction.

The investigational product will be dispensed at the discretion and by the direction of the Investigator in accordance with the conditions specified in this protocol. It is the Investigator’s responsibility to ensure that accurate records of investigational product issuance and return are maintained.

It is expected that the site staff will maintain refrigerator temperature logs in the investigational product storage area, recording the temperature at least once each working day. Excursions in temperature during storage should be discussed with the Chiltern CRA immediately and study supplies should be quarantined and not administered until Novan provides approval for use. Other supplies will be stored at room temperature.

8.3 TREATMENT ASSIGNMENT AND BLINDING

Subjects will be randomized to SB204 4% or Vehicle Gel on a 1:1 basis through utilization of the IWRS. The evaluator and subject will be blinded to the subject's treatment.

8.4 UNBLINDING OF TREATMENT ASSIGNMENT

In the event that a subject should experience an adverse event for which it is medically required to break the blind in order to determine appropriate treatment, unblinding can be achieved by using the IWRS. A study subject for whom the blind is broken will be discontinued from the study. Although not required, the Investigator should contact the Chiltern Medical Monitor prior to breaking the blind.

8.5 INVESTIGATIONAL PRODUCT ACCOUNTABILITY

A trained study staff member will maintain an inventory of investigational product components. This will include:

- Dates and initials of person designated as responsible for the inventory of the investigational product
- Amount received including date
- Amount currently in refrigerator, 2-8 °C storage
- Pumps dispensed to each subject, identified at a minimum by a unique subject number
- Amount transferred to another location within the study site or destroyed — this should not occur without prior notification to Chiltern
- Non-study disposition (e.g., wasted, broken)
- Amount returned to Novan or designee, if applicable
- Amount destroyed, if applicable

All investigational product accountability forms and treatment logs must be retained in the Investigator's permanent study file. These records must be available for inspection by Novan and Chiltern, their designees or by regulatory agencies at any time.

8.6 RETURNS AND DESTRUCTION

Upon completion or termination of the study, the site will be instructed on return or destruction of clinical supplies.

9. RECORDS MANAGEMENT

9.1 DATA COLLECTION

The full details of procedures for data handling will be documented in the data management plan.

Source study records will be collected for each study subject and a study database will be maintained for all randomized study subjects.

Novan requires that the study database be verifiable with the subject's source study record. This requirement necessitates access to all original recordings and other records for each subject. The Investigator must therefore agree to allow access to subjects' records, and source data must be made available for all study data. Subjects (or their legal representatives) must also allow access to the subject's medical records. Subjects will be informed of the importance of increased record access and permission granted by signature on the informed consent document prior to any study procedures being performed.

Before the study database is formally submitted to Novan, the study monitor, the Chiltern Medical Monitor or other Novan staff may request copies of the subject's source study record for preliminary medical review.

The Investigator must keep written or electronic source documents for every subject participating in the clinical study. These records must include:

- Name
- Contact information
- Date of birth
- Sex
- Medical history
- Concomitant diseases
- Concomitant therapies/medication
- Study visit dates
- Performed examinations, evaluations, and clinical findings
- Investigational product administration
- AEs, SAEs, or pregnancy (as applicable)

Additionally, any other documents with source data must be included in the subject's source documents and must include at a minimum the subject's initials, study number and the date of the evaluation.

The data recorded during the course of the study will be documented in the study database. Subjects will authorize the use of their protected health information during the informed consent

process in accordance with the applicable privacy requirements. Subjects who deny permission to use and disclose protected health information will not be eligible to participate in the study. The Investigator will ensure that the study records and any other documents forwarded to Chiltern contain no mention of subject names.

Any amendments and corrections necessary will be undertaken in both the study records and the study database.

Regulatory authorities, Investigational Review Boards, Novan and Chiltern or their designees, may request access to all study records and other study documentation for on-site audit or inspection. The Investigator must guarantee direct access to these documents. The original set of study records will be kept by the site or an authorized designee in a secured area. Clinical data will be recorded in an electronic format for subsequent statistical analyses. Data files will be stored on electronic media with a final master data file kept by Novan after descriptive and statistical analyses and reports have been generated and are complete.

